13.2.2.1 Statistical Power

A preliminary power analysis was conducted to estimate the minimum detectable difference in the likelihood of OUD diagnosis (H1.1), naloxone rescue kit order (H1.2) and MOUD order or referral for treatment (H2.2) within 30 days of the index visit, and the number of days covered by a MOUD prescription in the 90 days post-index (H2.2) among patients cared for in OUD-CDS relative to UC clinics (see **Section 13.4**). The power analysis relied on conservative assumptions regarding the numbers of randomized clinics (10, 30, 50) and of eligible patients (50 or 100 per clinic); a range of clinic intraclass correlations consistent with those observed for other process measures at HealthPartners (i.e., $ICC_{clin} = 0.01, 0.03, 0.05$); and central tendency estimates for the outcomes (2%, 5%, 10% and 20% or 70, 50, 30 days not covered in UC). Power estimates will be updated after Sites 2 and 3 are selected and preliminary data to inform analysis assumptions become available.

Effect size estimates for the binary outcomes were calculated using the NIH group randomized trial sample size calculator.[48] The difference in days covered was estimated using the Poisson regression module of PASS 11 software[49] after calculating an effective sample size (i.e., $N_{eff} = (n \text{ clinics} * m \text{ patients per clinic}) / (1 + (m-1) * ICC_{clin})$). In addition, the Poisson model power analysis was conducted to estimate the minimally detectable decrease in days NOT covered in the 90 days to post-index among OUD-CDS relative to UC patients to ensure that the estimated days in both groups remained between 0 and 90 days.

Table 3 summarizes the minimum detectable increases in outcome rates among OUD-CDS relative to UC patients given the aforementioned assumptions. Assuming 30 randomized clinics with 50 high risk patients each, that 5% of UC patients have an OUD diagnosis within 30 days of their index visit and $ICC_{clin} = 0.03$, the H1.1 analysis would be powered (power=0.80, $\alpha_2 = 0.05$) to detect a difference if $\geq 11.35\%$ (odds ratio = 2.43) of OUD-CDS patients have an OUD diagnosis within 30 days of their index visit. For an event occurring among 10% of UC patients given the

same assumptions otherwise, an analysis would be powered to detect a difference if it occurs among $\geq 18.12\%$ (odds ratio = 1.99) of OUD-CDS patients. Having more patients per clinic (e.g., 30 clinics * 100 patients each = 3000 patients) results in a smaller detectable effect size (i.e., 17.18 OUD-CDS vs. 10% UC; odds ratio = 1.87) although randomizing more than the minimum 30 clinics (e.g., 50 clinics * 50 patients each = 2500 patients) would reduce the minimum detectable effect (i.e., 16.02 OUD-CDS vs. 10% UC; odds ratio = 1.72) further with fewer patients. Table 3 also demonstrates that site-specific analyses of the OUD-CDS treatment effect would be sufficiently powered to detect only large effect sizes (e.g., 26.73% vs. 10%; odds ratio = 3.28) with 30 randomized clinics.

Table 3. Minimum detectable increase in the proportion of OUD-CDS relative to UC patients to experience the H1.1, H1.2 and H2.1 outcomes at the index visit, assuming n=(50, 100) patients per clinic, m=(10, 30, 50) randomized clinics, ICC_{clin}=(.01, .03, .05) and 2%, 5%, 10%, 20% outcome rates in UC.								
UC %	2%	5%	10%	20%	2%	5%	10%	20%
	n patients / clinic = 50				n patients / clinic = 100			
ICC_{clin}	m=10 clinics (minimum site-specific)				m=10 clinics (minimum site-specific)			
0.05	15.86	21.97	30.19	43.77	14.52	20.52	28.60	41.98
0.03	12.89	18.54	26.73	40.08	12.07	16.91	24.56	37.79
0.01	9.86	15.11	22.62	35.51	8.42	13.08	20.08	32.50
ICC_{clin}	m=30 clinics (minimum study-wide)				m=30 clinics (minimum study-wide)			
0.05	8.01	12.89	19.84	32.10	7.32	12.15	19.03	31.18
0.03	6.85	11.35	18.12	30.52	6.12	10.62	17.18	29.08
0.01	5.46	9.80	16.22	27.80	4.74	8.80	14.93	26.28
ICC_{clin}	m=50 clinics				m=50 clinics			
0.05	6.14	10.73	17.27	29.09	5.85	10.17	16.66	28.41
0.03	5.40	9.64	16.02	27.62	4.95	9.10	15.33	26.8
0.01	4.45	8.49	14.59	25.86	3.94	7.84	13.68	24.75

Table 4 provides a comparable summary for the H2.2 outcome, days covered by a MOUD prescription in the 90 days post-index. The inverse of the H2.2 outcome was used to calculate the minimum detectable difference in MOUD coverage days to ensure that estimated decreases in days not covered (or, increases in days covered) remained between 0 and 90 days. Continuing with the assumptions from the prior examples, the H2.2 analysis would be sufficiently powered to detect a decrease in days not covered by a MOUD if UC patients had 50 of their 90 post-index days uncovered (40 covered) but OUD-CDS patients had at least 37.0 uncovered (53.0 covered) days.

Table 4. Minimum detectable decrease in 90 days post-index without a MOUD prescription among OUD-CDS relative to UC patients, assuming n=(50, 100) patients per clinic, m=(10, 30, 50) randomized clinics, ICC_{clin}=(.01, .03, .05) and 30, 50, 70 days not covered in UC.								
UC	RR	30	50	70	RR	30	50	70
	n patients / clinic = 50				n patients / clinic = 100			
ICC_{clin}	m=10 clinics (minimum site-specific)				m=10 clinics (minimum site-specific)			
0.05	0.615	18.5	30.8	43.1	0.638	19.1	31.9	44.7
0.03	0.665	19.9	33.4	46.5	0.695	20.9	34.8	48.6
0.01	0.731	21.9	36.4	51.2	0.775	23.2	38.7	54.2
ICC_{clin}	m=30 clinics (minimum study-wide)				m=30 clinics (minimum study-wide)			
0.05	0.760	22.8	38.0	53.2	0.775	23.3	38.8	54.3
0.03	0.739	22.2	37.0	51.7	0.813	24.4	40.6	56.9
0.01	0.836	25.1	41.8	58.5	0.864	25.9	43.2	60.5
ICC_{clin}	m=50 clinics				m=50 clinics			
0.05	0.809	24.3	40.5	56.6	0.822	24.7	41.1	57.5

0.03	0.836	25.1	41.8	58.6	0.852	25.6	42.6	59.7
0.01	0.871	26.1	43.6	61.0	0.893	26.8	44.7	62.5

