13.4 Significance Testing

The H1.1, H1.2 and H2.1 outcomes will be assessed 3 times for each patient – at the index visit (0 days), and 30 (for primary outcomes) and 90 days post-index. Outcomes that occur at an index visit will be coded as also having occurred by days 30 and 90. Similarly, outcomes that occur between days 1 and 30 will be coded as having occurred by days 30 and 90; and those occurring

between days 31 and 90 will be coded as having occurred by day 90. We expect that the documented actions that providers take will be overwhelmingly attributable to the index visit. Some actions that providers initiate at the index visit, such as placing a treatment referral order, may not be complete until considerations related to safety or availability are addressed. The primary outcome for H1.1, H1.2 and H2.1 will be assessed at 30 days so that these actions, likely initiated at the index visit, may be completed prior to assessing the outcome. It is possible that outcomes will not be documented for patients who have post-index visits within 90 days at non-participating clinics. We assume that these eventualities will be rare and equally likely across treatment groups.

Because virtually all of the information pertinent to the H1.1, H1.2 and H2.1 outcomes will be captured by the day 30 measure, the primary hypothesis test for these models will compare the likelihood of the day 30 outcome by treatment group. The primary hypothesis test for the H2.2 outcome will compare the likelihood of the day 90 outcome by treatment group. These comparisons will be evaluated using a two-sided test with a Type I error rate of 5%. Comparisons at other time points will aid understanding of how relative differences in OUD-CDS versus UC settings may increase or decrease in the short term. For example, OUD-CDS might initiate a course of provider actions that otherwise would not occur (increase) or merely hasten action that eventually takes place in UC settings (decrease).

The Aim 3 outcomes represent counts of events that accrue over the post-index observation periods. The event rates in OUD-CDS versus UC clinics will be evaluated using a two-sided test with a Type I error rate of 5%.

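### Table 4 (H2.2) makes no allowance for the number of clinics, unlike Table 3; within its own method the stated 80% power is about 77% at 30 clinics, and the worked-example cell does not follow the table's formula

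*Combined protocol and SAP*

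**What the plan says.** Section 13.2.2.1 (Statistical Power) sizes the primary outcomes by two routes. For the three binary outcomes (H1.1, H1.2, H2.1; Table 3) it uses the NIH calculator for group-randomised trials. For days covered by MOUD (H2.2; Table 4) it says: "The difference in days covered was estimated using the Poisson regression module of PASS 11 software[49] after calculating an effective sample size". The effective sample size is clinics times patients per clinic, divided by the usual design effect. No degrees of freedom or small-cluster allowance is mentioned for Table 4.

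Power of 0.80 and a two-sided alpha of 0.05 are given for the H1.1 example. They pass to Table 4 through the sentence "Continuing with the assumptions from the prior examples, the H2.2 analysis would be sufficiently powered to detect a decrease in days not covered". The example there is 50 uncovered days in usual care against 37.0 with the intervention, at 30 clinics x 50 patients and ICC 0.03. The text introduces Table 4 as the H2.2 counterpart of Table 3.

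Both tables label the 10-clinic rows as site-specific and the 30-clinic rows as the study-wide minimum. Section 13.3 plans a mixed model with clinic random intercepts for H2.2 and gives no degrees-of-freedom method.

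**The concern.** The treatment effect is judged against variation between clinics. With 30 clinics in two arms, about 28 degrees of freedom are available to estimate that variation; with 10 clinics, about 8. Shrinking the patient count by the design effect puts the right variance into the formula. It does not account for that variance being estimated from few clinics, so normal quantiles give a detectable effect that is too small for the stated power.

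Table 3 appears to make this allowance and Table 4 does not, and the text does not tell the reader. H2.2 is one of four primary outcomes, and its detectable difference will be compared directly with those for the other three.

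**Working it through.** **Inputs** (section 13.2.2.1): 10, 30 or 50 clinics (k); 50 or 100 patients per clinic (m); ICC 0.01, 0.03, 0.05; power 0.80; two-sided alpha 0.05. Allocation is 1:1 (section 2.2).

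**1. Reproducing Table 4.** N_eff = k·m / (1 + (m − 1)·ICC). The standard Poisson-regression formula for a 1:1 binary covariate and base rate 1 is

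N_eff = [z(0.975)·√4 + z(0.80)·√(2 + 2/RR)]² / (ln RR)²,

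with z = 1.960 and 0.842. Solved for RR, it reproduces 17 of the 18 printed rate ratios to three decimals. Normal-quantile power at those 17 printed values is 79.9–80.3%. Three alternatives were tried at 30 x 50, ICC 0.05 (printed 0.760) and do not match: a Wald variance gives 0.748, t quantiles give 0.752, and a Poisson mean of 50 gives a value near 0.97.

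**2. Reproducing Table 3.** The two-proportion formula on N_eff/2 per arm, with variance p1q1 + p2q2, was run with normal quantiles and with t quantiles on k − 2 degrees of freedom:

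| Cell | Printed | t | Normal |
|---|---|---|---|
| 30 x 50, ICC 0.05, UC 10% | 19.84 | 19.82 | 19.44 |
| 30 x 100, ICC 0.01, UC 10% | 14.93 | 14.93 | 14.74 |
| 50 x 50, ICC 0.03, UC 10% | 16.02 | 16.02 | 15.89 |
| 10 x 50, ICC 0.03, UC 20% | 40.08 | 40.09 | 37.49 |
| 10 x 50, ICC 0.05, UC 2% | 15.86 | 17.07 | 14.46 |

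In the 30- and 50-clinic blocks, t matches 47 of 48 cells within 0.12 points. The exception is 30 x 50, ICC 0.03, UC 20%: printed 30.52, formula 30.14. In the 10-clinic block the match is looser, especially at low UC rates, as the last row shows, though the printed values are generally nearer t than normal.

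**3. Putting t into Table 4.** Power at a given RR is

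T_df{ [√N_eff·|ln RR| − 2·t(0.975, df)] / √(2 + 2/RR) }, df = k − 2.

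Example, 30 x 50, ICC 0.05: N_eff = 1500/3.45 = 434.8; √434.8 × |ln 0.760| = 5.72; √(2 + 2/0.760) = 2.152. With normal quantiles, (5.72 − 3.92)/2.152 = 0.84, or 80%. With t on 28 df (critical value 2.048), (5.72 − 4.10)/2.152 = 0.755, or 77.2%.

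| Clinics | Power with t at printed RR |
|---|---|
| 10 (site-specific) | 69.0–69.8% |
| 30 | 77.2–77.3% in five of six cells |
| 50 | 78.3–78.7% |

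At the unrounded rate ratios from the normal formula, 50 clinics give 78.4%. Rate ratios detectable at 80% power:

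| Cell | Printed | With t |
|---|---|---|
| 30 x 50, ICC 0.05 | 0.760 | 0.752 |
| 30 x 100, ICC 0.03 | 0.813 | 0.807 |
| 10 x 50, ICC 0.03 | 0.665 (33.4 days from 50) | 0.627 (31.4 days) |
| 10 x 50, ICC 0.05 | 0.615 | 0.573 |

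**4. The sixth 30-clinic cell.** For 30 x 50, ICC 0.03, N_eff = 1500/2.47 = 607.3. The normal formula gives 0.793 and t gives about 0.786 (39.3 days from 50). The printed value is 0.739, and the printed days follow it (0.739 x 50 = 37.0). Reading down the ICC column, the printed ratios run 0.760, 0.739, 0.836, whereas they should rise as the ICC falls. At 0.739, power is 94.8% with normal and 93.3% with t quantiles.

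**The case against.** - **The worked example.** The only H2.2 figure stated in the text is 37.0 days, and there power is about 93% even with t. This stands. Correcting that cell makes the stated difference more favourable (39.3 uncovered days, a smaller gap from 50), so it would be wrong to say that every printed figure is optimistic.
- **Materiality.** At 30 clinics the correction is 0.004–0.008 in rate ratio and under 3 power points, in an analysis that the protocol calls preliminary, with "conservative assumptions regarding the numbers of randomized clinics (10, 30, 50) and of eligible patients (50 or 100 per clinic". This stands too, and it limits the priority. However, the section promises updated estimates once Sites 2 and 3 are selected, and section 7.2 says that they have been, so a correction fits there.
- **The degrees of freedom are inferred.** True: clinics minus 2 comes from what fits Table 3, and that fit is loose at 10 clinics. Using clinics minus 4, to allow for care-system terms, still gives about 77% at 30 clinics. At 10 clinics it gives 64–66%, although an analysis within one system would have no system terms.
- **A base rate of 1 does not describe days.** Table 4 applies one rate ratio to 30, 50 and 70 uncovered days, so the day count never enters. A Poisson mean of 1 implies an SD equal to the mean. A 0–90 variable with mean 70 cannot have an SD above √(70 x 20) = 37.4, or above √(50 x 40) = 44.7 with mean 50; with mean 30 the limit is √(30 x 60) = 42.4, which exceeds 30. The true power could therefore lie on either side of the figures here. This stands in full.

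A reader might infer that the primary H2.2 test has only 69–70% power. The documents do not support that: those rows are site-specific, and section 13.2.1 plans at least 30 clinics. Nor do they support 77% as the power of H2.2 itself, for the base-rate reason above.

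**Conclusion.** The inconsistency is real. Table 4 uses normal quantiles on a deflated patient count; Table 3 behaves like t quantiles tied to the number of clinics. Within Table 4's own method, the 80% label corresponds to about 77% at 30 clinics, 78% at 50, and 69–70% in the 10-clinic rows. The one exception among the printed values is the worked-example cell, which departs from the table's formula. The swapped last two digits suggest a slip, but the documents do not confirm one.

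These figures rest on two assumptions: degrees of freedom of clinics minus 2, and the table's implicit Poisson mean of 1 per patient. They measure the effect of the missing allowance and do not establish the power for days covered, whose dispersion the documents do not give. Nor do they show that the trial is too small or that the planned mixed model is wrong. Priority is low to moderate: the study-wide effect is small, but a primary outcome's stated figures, including the one quoted in the text, need correcting.

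**What to change.** 1. Recompute all 18 rate ratios in Table 4, and the day counts that follow from them, with t quantiles on clinics minus 2 degrees of freedom, as Table 3 appears to do. State that rule for both tables.
2. Restate the worked example from the corrected table: about 0.786, or 39.3 uncovered (50.7 covered) days against 50 uncovered in usual care.
3. Add a sentence saying that Table 4 assumes a Poisson mean of 1 per patient and is not a power for the 0–90 day count itself.
4. Do not keep the printed values and relabel them 69–70%, 77% and 78%. That would be wrong for the worked-example cell and would give conditional figures a precision that they lack.
5. Recheck the Table 3 cell printed 30.52 (30 x 50, ICC 0.03, UC 20%); the formula that fits its neighbours gives about 30.14. No text relies on it.

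The cost is one table update and a few sentences. Seventeen Table 4 cells become slightly to moderately less favourable and the worked-example cell becomes more favourable. Enrolment, design and analysis are unchanged.

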13.3 Statistical Methods for Primary and Secondary Outcomes

This section provides an overview of the statistical methods to be employed in testing the primary and secondary outcomes. A more detailed description of the analysis may be found in the Statistical Analysis Plan. The Statistical Analysis Plan will provide more clarity about the underlying assumptions and methodological decisions regarding primary outcome analyses, including the extent to which either supplement alters the treatment effect.

Hypotheses for Aims 1 and 2 predict that the OUD-CDS intervention will increase the likelihood that patients at high risk of OUD are diagnosed with OUD (H1.1); and that among those at high risk or diagnosed with OUD it will increase the likelihoods that a naloxone rescue kit is ordered (H1.2) and that MOUD is ordered or the patient is referred to a provider who can order MOUD (H2.1), and the number of days covered by an MOUD prescription (H2.2). The hypotheses from Aims 1 and 2 will be tested using generalized linear mixed models so that the likelihood or counts of outcomes may be accurately estimated among OUD-CDS relative to UC clinics, accounting for the clustering of patients within randomized clinics. Binary outcomes (H1.1, H1.2, H2.1) will be normalized using a logistic-Normal link function, while it is anticipated that the count outcome (H2.2) will be normalized using a Poisson-Normal link function. The model will estimate fixed effects of OUD-CDS, care system and other covariates on outcomes, and random intercepts for clinics and patients (H1.1, H1.2, H2.1) or for clinics (H2.2).

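### Table 4 gives one rate ratio per row for uncovered days, so its differences do not carry a common 80% power for the planned H2.2 test on days covered, and the 0.739 cell does not reproduce

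*Combined protocol and SAP*

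**What the plan says.** Sections 7.1 and 13.1.2 define primary outcome 4 as total days covered by an MOUD prescription in the 90 days after index. Section 13.3 treats days covered as the count to be modelled: "it is anticipated that the count outcome (H2.2) will be normalized using a Poisson-Normal link function", with random intercepts for clinics. Section 13.4 sets a two-sided 5% test.

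Section 13.2.2.1 computes the detectable effect with the "Poisson regression module of PASS 11 software[49] after calculating an effective sample size". It targets "the minimally detectable decrease in days NOT covered in the 90 days to post-index among OUD-CDS relative to UC patients", so that estimates stay between 0 and 90 days, and describes the substitution openly: "The inverse of the H2.2 outcome was used to calculate the minimum detectable difference in MOUD coverage days". It treats a decrease in uncovered days and an increase in covered days as the same result.

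Table 4 has one rate ratio (RR) per row, applied to UC means of 30, 50 and 70 uncovered days. The worked example begins "Continuing with the assumptions from the prior examples", which means 30 clinics, 50 patients each, ICC 0.03 and 80% power. It takes UC at 50 uncovered days and calls 37.0 uncovered (53.0 covered) detectable. The row behind it prints RR 0.739 and 22.2 / 37.0 / 51.7 days.

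**The concern.** A ratio on a log scale does not carry over to the complement of a bounded variable. A fall from 30 to 23.8 uncovered days is a ratio of 0.793; the matching rise from 60 to 66.2 covered days is a ratio of 1.103. Power for one is not automatically power for the other.

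Table 4 also uses the same ratio whatever the UC mean. A Poisson calculation cannot do that unless the mean has dropped out of it, so the spread of the outcome has been fixed by the method and not by anything known about MOUD days.

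At stake is what a reader may conclude about one of four primary outcomes. If the tabled differences do not share 80% power, the table cannot be used to judge what H2.2 can detect, and the error changes direction across the columns.

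**Working it through.** **Inputs.** Section 13.2.2.1: 30 clinics, 50 patients per clinic, ICC 0.03, power 0.80 (stated in the H1.1 example and carried forward), N_eff = clinics × m / (1 + (m − 1) × ICC). Section 13.4: two-sided 0.05. Section 2.2: 1:1 allocation. The Poisson base mean is not stated; 1 is inferred below.

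**1. Reproduce Table 4.** Poisson regression with a binary covariate:

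N_eff × base mean × (ln RR)² = [1.96 × 2 + 0.8416 × √(2 + 2/RR)]²

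With base mean 1:

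- 10 × 50, ICC 0.05: N_eff = 500/3.45 = 144.9, RR 0.615 (printed 0.615)
- 30 × 50, ICC 0.01: N_eff = 1500/1.49 = 1006.7, RR 0.836 (printed 0.836)
- 50 × 100, ICC 0.03: N_eff = 5000/3.97 = 1259.4, RR 0.852 (printed 0.852)

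Seventeen of the 18 printed ratios reproduce to three decimals. With a base mean of 30 to 70 days the base-case ratio would be about 0.959 to 0.973, so those means were not used.

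**2. The exception is the cell behind the worked example.** N_eff = 1500/(1 + 49 × 0.03) = 607.3 gives RR 0.793; the table prints 0.739. Within its block the printed ratios run 0.760, 0.739, 0.836 as the ICC falls from 0.05 to 0.01, when they should rise steadily. Power at 0.739 by the table's own method:

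Φ{[√607.3 × |ln 0.739| − 3.92] / √(2 + 2/0.739)} = Φ(1.63) = 95%

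Other two-sided variance choices give 93% to 96%. With 0.793 the row becomes 23.8 / 39.7 / 55.5, and the example 39.7 uncovered (50.3 covered).

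**3. What base mean 1 implies.** A Poisson variable with mean 1 has SD 1, so in days the SD equals the mean: 30, 50 and 70. A 0-90 variable with mean u has SD at most √(u × (90 − u)): 42.4, 44.7 and 37.4. The implied SD is possible at 30 and impossible at 50 and 70.

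**4. Change of scale, keeping the table's method.** On covered days the detectable ratio at N_eff 607.3 is 1.251.

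| UC uncovered / covered | Detectable days, uncovered scale | Detectable days, covered scale |
|---|---|---|
| 30 / 60 | 6.2 | 15.1 |
| 50 / 40 | 10.3 | 10.0 |
| 70 / 20 | 14.5 | 5.0 |

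The scales agree near the midpoint and part at the ends. The 15.1 is not credible as a requirement: base mean 1 on 60 covered days means an SD of 60, above the maximum of 42.4.

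**5. Power under a possible SD.** Let every patient have 0 or 90 days, the largest possible variance (an assumption that gives a bound). With u the UC mean and t = 0.793u:

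SE = √{[u(90 − u) + t(90 − t)] / (607.3/2)}; power = Φ(difference/SE − 1.96)

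| u | t | Difference | SE | Power |
|---|---|---|---|---|
| 30 | 23.8 | 6.2 | 3.33 | 46% |
| 50 | 39.7 | 10.3 | 3.63 | 81% |
| 70 | 55.5 | 14.5 | 3.30 | 99% |

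This comparison of means is the same for covered and uncovered days. A robust-variance log-ratio test also gives almost equal power on the two scales: 45.5% and 45.7%, 80.2% and 80.2%, 98.9% and 98.7%.

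**6. Detectable difference in mean days covered, maximum SD.** 2.80 × 2 × SD/√607.3 with SD 42.4, 44.7 and 37.4 gives about 9.6, 10.2 and 8.5 days.

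**The case against.** The substitution is disclosed and a reason is given. Section 13.2.2.1 calls the analysis preliminary and promises an update. It also says that the difference in days covered was estimated and the uncovered calculation was made in addition; only the uncovered results are tabulated. Section 13.3 merely anticipates a Poisson-Normal model and leaves detail to a Statistical Analysis Plan. The base case is a stated minimum: section 13.2.2 expects that many clinics could reach 1,000 patients, and section 14.3.1 expects more than 10,000 patients overall.

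Much of this stands, and it limits the consequence: nothing in the trial's size depends on Table 4. It does not mend the table. Updating the inputs within the same method would keep one ratio per row.

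A reader might go further and infer that the change of scale spoils every cell, or that the planned test has about 22% power when UC has 30 uncovered days (the table's own method applied to covered days at ratio 0.793). The documents support neither. At 50/40 the power is 80% on one scale and 82% on the other. The 22% rests on the impossible SD of 60; even at the maximum SD the power is about 46%. It also uses the recomputed ratio; at the printed 0.739 the same method gives about 32%, 95% and over 99% on covered days.

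**Conclusion.** Table 4 does not give differences that share 80% power for the H2.2 test described in section 13.3. The main cause is one ratio per row, which ties the SD to the UC mean; the switch to uncovered days adds to it only while that device is kept. In the base case, under the largest possible SD, the 30-uncovered column can be optimistic (6.2 tabled by the table's method against 9.6 days needed), the 50 column is about right (10.3 against 10.2), and the 70 column is pessimistic (14.5 against 8.5).

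Separately, the 0.739 cell is wrong by the table's own method, which gives 0.793. The error runs into 22.2 / 37.0 / 51.7 and the worked example.

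Assumptions: base mean 1 is inferred from 17 matching cells; the power figures use the all-or-none bound, equal allocation and the plan's N_eff. The document gives no SD or dispersion for days covered, so the actual power of the planned test cannot be fixed from it, and a conclusion that H2.2 is underpowered would not follow.

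**What to change.** 1. Recompute Table 4 as the detectable difference in mean days covered for each UC mean, using N_eff and a stated SD or dispersion for days covered from existing EHR data. Until that is available, give the maximum-SD bound: about 9.6, 10.2 and 8.5 days in the base case.
2. Correct 0.739 to 0.793, its row to about 23.8 / 39.7 / 55.5, and the worked example to about 39.7 uncovered (50.3 covered), worded as at most that many uncovered days. If the table is recomputed under item 1, draw the example from the new table.
3. State the same scale, and the dispersion assumed, in sections 13.2 and 13.3. Moving the analysis to uncovered days merely to match Table 4 would leave the single-ratio fault in place.

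The cost is one recalculated table and a few sentences, with no extra patients. Some stated figures become less favourable, notably in the 30-uncovered column.
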